Eligible subjects will be invited to the Laboratory for Rehabilitation Neuroscience. We will obtain IRB approved informed consent. Subjects will be explained in detail about the procedures outlined for the study. In order to characterize the current clinical progression of disease we will administer a subset of the following assessments: Montreal Cognitive Assessment (MoCA), Beck Depression Inventory (DBI), Ambulatory Parkinson's Disease Monitoring (APDM), The Essential Tremor Rating Assessment Scale (TETRAS), and Toronto Western Spasmodic Torticollis Rating Scale (TWSTRS). Once completed, subjects will be fitted with an EEG cap and have the electrode holes of the cap filled with conductive gel. The electrodes will be placed and then resting-state EEG and/or task-based EEG will be collected. Resting-state EEG will have subjects sit down and rest, without falling asleep, for no longer than 20 minutes. Task-based EEG will have subjects perform a pinch grip task lasting no longer than 30 minutes. For the pinch grip task, subjects will be signaled to produce a pre-determined amount of force on loadcells using one hand. They will be provided with visual feedback on a screen so that they may see how much force they are producing relative to the target force. Once the EEG procedure is conducted, the rTMS intervention will be administered to the targeted region for only the patient groups. Afterwards, the same EEG procedure conducted before the rTMS will be performed to capture the effects of the intervention. Once completed, the waiting period will occur. Once the period ends, the EEG procedure will occur again. Controls will perform all tasks except for the rTMS intervention.

Outcome measures: The primary outcome measure will be EEG cortical recordings. EEG is an electrophysiological imaging method used to record electrical activity of the brain. It is non-invasive and provides information about the behavior of neuronal populations below the scalp. This is useful to our study because we expect rTMS to alter the excitability of neurons in the motor cortex. We will also collect electromyography (EMG) data from hand and neck muscles as a secondary measure.

Clinical assessments: We will use certain clinical assessments to characterize the mental state, mental ability and motor symptoms of subjects enrolled in this study.

(1) The Montreal Cognitive Assessment (MoCA) is a widely used screening tool for detecting cognitive impairment and mild cognitive impairment.

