Statistical analysis will be done with R, a free software environment for statistical computing and graphics, and Matlab toolboxes (EEGLAB, among others). For the resting state data, we will use a mixed model ANOVA on the average power of different frequency bands. There will be 2 factors: group (Controls, and tremor groups) and time (3 levels: T0, T1, and T2), where T0 is data collected before rTMS, T1 is data collected after rTMS, and T2 is data collected after the waiting period. For task-based data, we will use EEGLAB to preprocess the data and compute Event Related Spectral Perturbations (ERSPs), a time-spectral graph. From the ERSPs we will run comparisons at each time-frequency point. Because of the large quantity of time-frequency points, we will correct for multiple comparisons.

From previous work [3] we have data about the mean and standard deviation of the average power of the beta band (12-30 Hz) of activity in the brain of ET patients during a force control task similar to the one proposed for this study. We expect to have 3 groups (controls, dystonia and tremor) each built of approximately 30 people. We conducted a power analysis comparing ET vs. control using an independent samples t-test (alpha = 0.05; two-tailed). With this data we predict a 95% power estimate.

	ET		Controls		Power
	Mean	SD	Mean	SD	Estimate
Average beta band (12-30 Hz) power	-2.24	1.57	-3.57	1.24	94.7%

Possible Discomforts and Risks:

There are some possible discomforts and risks for participants taking part in this study.

TMS:

• Headaches – Headaches and neck aches can occur. They can be related to stabilizing the neck when measuring TMS. They are usually short lasting and respond easily to over the counter analgesics.

- Transient hearing threshold shift There is a possibility of temporary mild hearing loss due to the noise of the TMS machine. The rate of this risk is unknown yet. Earplugs will be provided to the participant to reduce the potential for this risk.

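### The only power calculation uses average beta power during the force task, but no planned analysis tests that average; separately, the primary outcome names no measure

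*Combined protocol and SAP*

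**What the plan says.** The outcome statement, under Outcome measures, reads: "The primary outcome measure will be EEG cortical recordings". Study Design likewise names EEG as the primary outcome measure and goes no further.

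The analysis is set out under Regulatory Approval and Statistics, in two parts:

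- For resting data, "we will use a mixed model ANOVA on the average power of different frequency bands", with group and time (T0, T1, T2) as factors. The bands are not listed, and the group factor is described as controls and tremor groups.
- For task data, event-related spectral perturbations (ERSPs) are computed, and then "From the ERSPs we will run comparisons at each time-frequency point". A correction for multiple comparisons is promised, but neither the method nor the number of points is given.

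The same section bases power on "the mean and standard deviation of the average power of the beta band (12-30 Hz) of activity in the brain of ET patients", measured "during a force control task similar to the one proposed for this study". The test is also stated: "We conducted a power analysis comparing ET vs. control using an independent samples t-test (alpha = 0.05; two-tailed". On group size: "We expect to have 3 groups (controls, dystonia and tremor) each built of approximately 30 people". The table gives ET -2.24 (SD 1.57), controls -3.57 (SD 1.24) and power 94.7%, which the text rounds to 95%.

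**The concern.** A power statement is useful when it describes a test the trial will run. Here the powered variable is one number per person, a band average taken during the task. The plan forms band averages only from resting data and analyses task data only as a grid of points. The variable with documented means and SDs falls between the two.

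Separately, the outcome statement names a recording rather than a measure. It does not say whether rest or task, which band, which region or which time window decides the aims. Correcting for multiplicity within one ERSP map does not cover the choice among these. Both aims ask whether patients' cortical activity shifts towards that of controls, and the plan does not say which result would answer that. A reader of the final report could not tell a prespecified primary result from one chosen after the maps were seen, and might attach the 95% to a test it was never calculated for.

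**Working it through.** **1. Reproduce the stated power.** All inputs come from the power paragraph and table under Regulatory Approval and Statistics: means -2.24 and -3.57, SDs 1.57 and 1.24, about 30 per group, two-sided alpha 0.05. No dropout is stated, so none is assumed.

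- Difference: -2.24 - (-3.57) = 1.33
- Pooled SD: sqrt((1.57² + 1.24²)/2) = sqrt((2.4649 + 1.5376)/2) = 1.415
- Standardised difference: d = 1.33/1.415 = 0.94
- Noncentrality: d × sqrt(30/2) = 0.94 × 3.873 = 3.64, with 30 + 30 - 2 = 58 degrees of freedom
- Power from the noncentral t distribution: 94.7%

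This matches the table. A Welch test also gives 94.7%, and the normal approximation gives 95.4%. The arithmetic is sound.

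**2. Match the powered test to the planned analyses.**

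| | Powered test | Planned, rest | Planned, task |
|---|---|---|---|
| Condition | Force task | Rest | Pinch task |
| Variable | Average 12-30 Hz power | Average power, bands unnamed | ERSP value at each point |
| Test | One two-sample t-test, ET vs control | Mixed model ANOVA, group and time | Comparisons at every point, corrected |

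The resting analysis has the right kind of variable in the wrong condition. The task analysis has the right condition with a different variable and a different error threshold. Neither column matches the first.

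**3. Illustrate why the figure does not carry over.** Three assumptions are needed that the documents do not supply: the same d = 0.94 at one prespecified point, a Bonferroni correction, and m effective tests. With 30 per group and alpha = 0.05/m:

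| m | Power at that point |
|---|---|
| 1 | 94.7% |
| 10 | 76.1% |
| 50 | 57.2% |
| 100 | 48.9% |
| 1000 | 25.2% |

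These values show only that the power of a corrected pointwise test depends on quantities the plan leaves open. They are not estimates of this plan's power. A cluster-based correction would lose less, the effect at a single point could be smaller than for the average, and the chance that at least one of many affected points is detected would be higher than the chance at one point.

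**4. What cannot be computed.** The aims concern the change from before to after stimulation relative to controls. The documents give no expected change and no within-person correlation, so power for that contrast cannot be derived for any choice of endpoint.

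**The case against.** The strongest reply is that task beta is analysed. Nothing excludes 12-30 Hz from the ERSP comparisons, so a reader who infers that beta activity during the task is ignored would be wrong. That stands. What is missing is a test of the average, and power for one test of an average does not transfer to many corrected tests of points.

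A second reply is that the analyst's freedom is bounded. The introduction reports attenuated alpha and beta changes over the motor cortices during force control, and the aims fix the direction as a shift towards controls. This stands in part: the choice is not unlimited. But the analysis text still leaves the bands unnamed, and the procedures allow resting EEG, task EEG or both.

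Third, choosing beta during the task over alpha or rest is partly a matter of judgement. That is fair. The documents do not show that it is the most sensitive measure, and nothing in them ranks measures by response to rTMS. The case for it is narrower: it is the only variable with means and SDs in the protocol and the only one with a power figure.

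Finally, making this average primary does not turn 95% into the power of the group-by-time test. That is correct, and the protocol should say so.

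**Conclusion.** The point holds and should be corrected. The only power figure in the protocol is right as arithmetic, but it belongs to a test the plan does not contain. The unspecific primary outcome is a second gap alongside it. A reader might take it as a consequence of the pointwise testing, but the two are independent, and curing one would not cure the other.

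Three stronger readings are not supported. Task beta is not left out, since it is covered pointwise. The trial was not shown to be underpowered: the range of 25% to 76% in the illustration rests on an assumed Bonferroni correction, assumed numbers of tests from 10 to 1000 and an assumed equal effect at a single point. And the sample size was not derived from this variable: the protocol calculates power for an expected group size.

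The conclusion does not rest on those assumptions. It follows from comparing the power paragraph with the two analysis descriptions in the same section.

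**What to change.** Amend Outcome measures and Regulatory Approval and Statistics as follows.

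- Name one primary endpoint: average 12-30 Hz power during the pinch task. Define the region and time window as in the prior ET study that supplied the means and SDs; the protocol now says only that the activity is in the brain.
- Take one value per participant at T0, T1 and T2, and analyse it with the group-by-time mixed model already planned for rest. Name controls, dystonia and tremor as the groups, because the present description of the group factor does not name dystonia although Specific Aim 1 concerns it.
- Make the ERSP maps, the other bands and resting-state power secondary.
- State that 94.7% applies only to the cross-sectional ET-control t-test on this average at baseline, and that power for the pre-to-post shift is not established.

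The text change is a few sentences, and the analysis needs one summary value per recording. There are two real costs. Task EEG must be collected from every participant, whereas the procedures now make it optional. And effects in other bands or at rest can no longer be presented as primary. The planned sample size does not change.

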Protocol

Title: Changes in Cortical Oscillations Induced by rTMS Therapy in Patient Populations with Tremor

Principal Investigator: [name]

Principal Co-Investigator: [name] [name]

Sub-Investigator: [name] Sub-Investigator: [name] Sub-Investigator: [name]

Dystonia is a movement disorder characterized by sustained or intermittent muscle contractions causing abnormal movements and/or postures [1]. In some patients, they experience both the dystonic symptoms and also an oscillating tremor and these patients are referred to as having dystonic tremor (DT). Here, the contractions are intermittent and oscillatory, and movement can appear rhythmical. When DT appears in the arms, it is similar to symptoms of another movement disorder called essential tremor (ET). Sometimes, DT and ET can be misdiagnosed. These disorders are associated with a loss of inhibition along different levels of the central nervous system. Noninvasive modalities of brain stimulation that can modulate cortical excitability, such as repetitive Transcranial Magnetic Stimulation (rTMS), have been proposed as an alternative therapeutic opportunity to correct the loss of inhibition. However, studies analyzing the effects of rTMS on dystonia populations have shown contradictory results [2], ranging from mild to non-detectable clinical benefit over short periods of time. Many of these studies use clinical scales as the only outcome measure, which may not be sensitive enough to capture minor changes in cortical activity. These inconclusive findings have complicated what future directions to take with this approach. Therefore, there is merit in assessing whether any therapeutic change is occurring in the cerebral cortex using more sensitive measures of the physiology.

In prior work [3][4], we have used high-density electroencephalography (EEG) to study DT and ET. We have found that in both groups, patients exhibit attenuated changes in alpha (7-12 Hz) and beta (12-30 Hz) band activity over the motor cortices during a force control task. Irregular activation of the motor cortices has also been confirmed in fMRI studies [5]. We propose using EEG as an outcome measure to detect changes in cortical oscillations caused by rTMS in patient populations with tremor. The near millisecond resolution of EEG will allow us to detect changes in distinct frequency bands in signals recorded from the cortex.

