The **primary goal** of this study is to compare differences in cortical activity of patients with dystonia and/or tremor before and after applying a session of rTMS. Specifically, we will apply rTMS to the primary motor cortex (M1) as our group and others have shown abnormal function of the region. Moreover, a study [6] shows that targeting of M1 and the dorsal premotor cortex (dPMC) with rTMS results in a trend towards improved clinical outcome in patients with focal hand dystonia and cervical dystonia.

The **central hypothesis** of this study is that rTMS can modify cortical oscillations in patient populations with dystonia and/or tremor and that we will be able to detect these changes with the use of EEG. By applying inhibitory rTMS to the motor cortices, we may expect a shift in cortical oscillations towards normal activity.

Specific Aim 1: Determine therapeutic effect of rTMS on the cortex of patients with Dystonia

We will determine any therapeutic effect of a 1-Hz rTMS session on the primary motor cortex of patients with dystonia by comparing the differences in cortical activity of healthy controls and patients with dystonia pre-rTMS session to the differences in cortical activity of healthy controls and patients with dystonia post-rTMS session. We hypothesize that after the rTMS session, the cortical activity of patients with dystonia will shift towards the cortical activity of healthy controls.

Specific Aim 2: Determine therapeutic effect of rTMS on the cortex of patients with tremor

We will determine any therapeutic effect of a 1-Hz rTMS session on the primary motor cortex of patients with tremor by comparing the differences in cortical activity of healthy controls and patients with tremor pre-rTMS session to the differences in cortical activity of healthy controls and patients with tremor post-rTMS session. We hypothesize that after the rTMS session, the cortical activity of patients with tremor will shift towards the cortical activity of healthy controls.

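### The resting-state EEG tests cover several unnamed frequency bands with no stated multiplicity adjustment and no primary band or contrast, so their family-wise error is uncontrolled

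*Combined protocol and SAP*

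**What the plan says.** The analysis text is in Regulatory Approval and Statistics and treats the two kinds of EEG data separately.

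- Resting data: "For the resting state data, we will use a mixed model ANOVA on the average power of different frequency bands". The model is described as "There will be 2 factors: group (Controls, and tremor groups) and time (3 levels: T0, T1, and T2"). The bands are neither named nor counted, and no adjustment is mentioned.
- Task data: comparisons are made at every point of the event-related spectral maps, followed by "Because of the large quantity of time-frequency points, we will correct for multiple comparisons". Neither the method nor the error rate of this correction is given.

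Nothing elsewhere narrows the set of resting tests. Under Outcome measures, "The primary outcome measure will be EEG cortical recordings", without a band, region or contrast. There are two aims, each with its own hypothesis: "Specific Aim 1: Determine therapeutic effect of rTMS on the cortex of patients with Dystonia" and "Specific Aim 2: Determine therapeutic effect of rTMS on the cortex of patients with tremor". The background names two bands, reporting from earlier force-task work that "patients exhibit attenuated changes in alpha (7-12 Hz) and beta (12-30 Hz) band activity over the motor cortices", but does not present them as the resting-state list. A two-sided 0.05 level appears once, for the t-test in the power analysis.

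**The concern.** The reason given for correcting is the number of time-frequency points, and such points exist only in the task analysis. The sentence cannot fairly be stretched to the resting ANOVAs. Those are also repeated, at least twice, because the text speaks of bands in the plural.

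With no primary band or contrast, a significant group-by-time result in any one band could be reported in support of the central hypothesis that rTMS alters cortical oscillations. Because the list of bands is open, it could also be settled after the data are seen. A reader of the results would then have no way to judge how surprising one positive band is.

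**Working it through.** **1. The plan's own figure.** Inputs from the power table: ET mean −2.24 (SD 1.57), control mean −3.57 (SD 1.24), about 30 per group, two-sided 0.05.

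- Difference = 3.57 − 2.24 = 1.33. Pooled SD = √[(1.57² + 1.24²)/2] = 1.415. Standardised difference d = 1.33/1.415 = 0.94.
- Noncentral t with 58 degrees of freedom and noncentrality 0.94 × √(30/2) gives power 94.7%.

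This matches the plan. It concerns beta power during the task, ET against controls, and is not a calculation for the resting group-by-time interaction.

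**2. Error rate if tests were independent.** With k tests at 0.05, the chance of at least one false positive is 1 − 0.95^k:

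- k = 2: 9.8%
- k = 4: 18.5%
- k = 5: 22.6%
- k = 10: 40.1%

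These are reference values only. Bands measured in the same people are likely to be correlated, and the two patient–control comparisons share the controls.

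**3. Error rate allowing for both.** The group-by-time interaction F test was simulated with no true effect: 20,000 runs per setting, 30 people in each of three groups, three times (T0, T1, T2), normal errors, 0.05 per test, and between-band correlation of 0, 0.5 or 0.8. The F test has (G−1)(3−1) and (N−G)(3−1) degrees of freedom for G groups and N people: 4 and 174 with three groups, 2 and 116 with two. Entries are the chance of at least one significant interaction.

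| Model | Bands (assumed) | Correlation 0 | 0.5 | 0.8 |
|---|---|---|---|---|
| One three-group ANOVA per band | 1 | 5.1% | 5.1% | 4.9% |
| | 2 | 9.6% | 8.8% | 8.1% |
| | 4 | 18.8% | 16.3% | 12.0% |
| | 5 | 22.0% | 18.7% | 13.5% |
| Separate dystonia–control and tremor–control ANOVAs per band | 1 | 9.4% | 9.1% | 8.8% |
| | 2 | 17.2% | 16.4% | 14.3% |
| | 4 | 31.7% | 27.3% | 21.1% |
| | 5 | 38.2% | 31.8% | 22.8% |

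The first row is a check: a single test holds its 5%. Simulation standard error is about 0.15 points near 5% and 0.35 points near 38%. Only the interaction is counted; also reading main effects, or T1 and T2 contrasts, without adjustment would add to these rates.

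**4. Power at stricter levels.** The calculation in step 1 at smaller two-sided levels gives 90.7% at 0.025 (the first Holm step for two bands) and 85.2% at 0.0125 (two bands in each of two aims, adjusted together). For five bands it gives 83.2% at 0.01. These values illustrate the cost; they do not measure it for the resting interaction.

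**The case against.** Several objections are sound and limit what can be claimed.

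- *The size is not fixed by the plan.* A reader might infer that the false-positive rate is far above 5%. The documents do not establish that. The number of resting bands is unstated, and only two bands are named anywhere. With two bands and one three-group ANOVA per band, the rate is 8.1% to 9.6%.
- *The 0.05 level is an inference.* A reader might take it that the plan tests every band at 0.05. That level is given only for the power-analysis t-test, although no other level appears.
- *Doubling for two aims is an inference.* The group factor is written as controls and tremor groups. The text does not say whether each aim has its own model, and a single three-group interaction test would not double the count. The independent-test values of 18.5% and 40.1% also ignore the shared controls; no simulated two-band or five-band setting reached them.
- *Direction matters for the aims.* Both aims predict a shift towards healthy controls, so a significant change away from them would not support either. The simulated rates count both directions. For a single T0-to-T1 contrast, counting only the favourable direction gives about 2.5% per test, and two independent bands give 1 − 0.975² = 4.9%. The rate still roughly doubles relative to one test, and the central hypothesis as worded is satisfied by any change.
- *Comparison with the task analysis.* A reader might conclude that the resting results face a weaker standard of proof. This cannot be shown, because the task correction's method and error rate are not given.
- *The study is mechanistic, and resting data may not exist for everyone.* The procedures allow resting recording, task recording or both, and the only power calculation is for task data. This lowers the weight of the point. It does not remove it, since the protocol states hypotheses for both aims and nowhere calls the resting analysis exploratory.

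The omission itself stands: no adjustment, no band list, and no primary contrast for the resting data.

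**Conclusion.** The concern holds in a limited form. The resting-state family of tests is undefined and no adjustment is stated for it, so its family-wise error is uncontrolled. Counting any significant group-by-time interaction at 0.05, the error rate exceeds 5% in every setting examined with two or more bands:

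- about 8–10% for two bands with one three-group ANOVA per band;
- about 14–17% for two bands with separate comparisons sharing controls;
- about 23–38% for five bands with separate comparisons.

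The assumptions are 0.05 per test, two to five bands, between-band correlation of 0 to 0.8, and 30 people per group. The plan supports the last as an approximate target, the first only by analogy with its power analysis, and the other two not at all. The gap should be closed before analysis; it does not undermine the design.

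**What to change.** Amend Regulatory Approval and Statistics to cover four points.

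1. List the resting bands before any analysis, for example the alpha and beta bands of the background.
2. State the model: one three-group ANOVA per band or a separate model per aim, with dystonia named in the group factor.
3. Name the primary resting test for each aim as the difference between patients and controls in change from T0 to T1.
4. State the significance level and the adjustment.

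Possible wording:

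> For resting-state data, the group-by-time contrast of T1 with T0 will be tested in [listed bands] for dystonia versus controls and for tremor versus controls. Within each aim, p-values will be Holm-adjusted across bands at a two-sided level of 0.05. Results at T2 and any unadjusted band results will be reported as exploratory.

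Treating each aim as its own family suits two separate conclusions. It leaves the chance of a false finding in either aim at up to 1 − 0.95² = 9.75% if the aims were independent. If one overall claim about the central hypothesis is to be made, Holm adjustment should run across bands and aims together.

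The cost is a few sentences, negligible computing, and some loss of power per band. The plan's task-beta example falls from 94.7% at 0.05 to 90.7% at 0.025. The loss for the resting interaction cannot be computed from the documents. A short band list keeps it small.

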Study Design: Subjects diagnosed with Dystonia and/or tremor will be enrolled. Diagnosis of Dystonia and tremor will be established in accordance with the Consensus Statement of the Movement Disorders Society [1]. In this study, we plan to recruit up to 60 subjects with Dystonia and/or tremor in the age range of 21-80 years. Specifically, our inclusion criterion is: Diagnosis of Dystonia and/or tremor according to the Consensus Statement of the Movement Disorders Society. We will exclude patients with 1) pregnancy; 2) active seizure disorder; 3) presence of a metallic object such as a pacemaker, implants, metal rods, and hearing aid, 4) history of stroke. We will also identify subjects who meet inclusion/exclusion criteria from the IRB approved INFORM database (IRB#201501166). These subjects have consented to being contacted for future research. We will enroll up to **30 healthy controls** of similar age distribution and sex ratio as the Dystonia and/or tremor group for normative electrophysiological data. Controls will be recruited through fliers placed across campus. Additionally, we will use databases to identify healthy controls that are willing to be contacted through Health Street and Consent2Share. Controls must be free from a diagnosed neurological disorder. We will exclude controls with 1) pregnancy; 2) active seizure disorder; 3) presence of a metallic object in their brain, 4) any history of stroke.

Electroencephalography (EEG) will be used as the primary outcome measure. Repetitive Transcranial Magnetic Stimulation (rTMS) will be used over the motor cortices as an intervention that is expected to have short-term (less than an hour) electrophysiological effects. EEG will be collected before and after administration of rTMS. A waiting period will follow to allow the short-term effects of the intervention to subside, after which a third EEG procedure will be repeated.

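### Does the plan need a written rule for which analysis group holds patients who have both dystonia and tremor?

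*Combined protocol and SAP*

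**What the plan says.** The inclusion criterion under Study Design is "Diagnosis of Dystonia and/or tremor according to the Consensus Statement of the Movement Disorders Society". It admits up to 60 patients, alongside up to 30 healthy controls. The two aims are headed "Specific Aim 1: Determine therapeutic effect of rTMS on the cortex of patients with Dystonia" and "Specific Aim 2: Determine therapeutic effect of rTMS on the cortex of patients with tremor". Each compares patients with controls before and after stimulation, and neither excludes patients who also have the other condition.

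Regulatory Approval and Statistics describes the resting-state mixed model ANOVA this way: "There will be 2 factors: group (Controls, and tremor groups) and time (3 levels: T0, T1, and T2". The next paragraph, on power, gives the group structure: "We expect to have 3 groups (controls, dystonia and tremor) each built of approximately 30 people".

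The opening background describes patients with dystonic symptoms together with an oscillating tremor and says "these patients are referred to as having dystonic tremor (DT".

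**The concern.** A between-subject group factor puts each person in one level, yet the two aim populations overlap. A patient with DT has dystonia (Aim 1) and tremor (Aim 2), and no sentence says which level holds that patient. The ANOVA label does not help, because it names controls and tremor groups without listing the levels or mentioning dystonia.

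Some wording also points away from dystonia. The background says the earlier EEG work was used "to study DT and ET. We have found that in both groups, patients exhibit attenuated changes", which treats DT and ET as a pair. It then states the purpose as to "detect changes in cortical oscillations caused by rTMS in patient populations with tremor", close to the study title.

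At stake is who enters the dystonia-versus-control and tremor-versus-control contrasts, for both resting-state and task-based data. If the placement stayed open until the EEG results were known, it could be chosen to suit them.

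**Working it through.** **Inputs.** Up to 60 patients and up to 30 controls (Study Design). Three groups of about 30; ET mean -2.24 (SD 1.57), control mean -3.57 (SD 1.24); independent-samples t-test, two-sided 0.05; stated power 94.7% (all from Regulatory Approval and Statistics). The number of patients with both conditions, k, is not given.

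**1. The plan's own figure.** Difference = -2.24 - (-3.57) = 1.33. Pooled SD = sqrt((1.57² + 1.24²)/2) = sqrt(2.00125) = 1.415. Standardised difference = 1.33/1.415 = 0.940. With 30 per group, noncentrality = 0.940/sqrt(2/30) = 3.64 on 58 degrees of freedom, and power = 94.74%. This matches the table. The inputs concern ET and controls, so the figure does not depend on where DT patients go as long as the tremor group stays near 30.

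**2. Head count.** 3 × 30 = 90 = 60 + 30. If patients with both conditions were counted under both aims, the two patient populations would total 60 + k. The planned numbers therefore suggest, though with approximate and upper-limit figures they do not prove, that each patient is counted once.

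**3. Which way the text leans.**
- Toward dystonia: the background starts from dystonia, introduces DT as a presentation in some of those patients, and then contrasts it with ET as a different disorder. The power analysis uses ET for the tremor comparison.
- Toward tremor, or a separate level: the pairing of DT with ET describes groups in prior work, not levels in this analysis. The phrase about populations with tremor cannot define a tremor level, because the same study enrols dystonia. The ANOVA label is loose, and the three groups named in the next paragraph largely settle it.
- Neutral: the Clinical assessments section links two rating scales to ET and cervical dystonia, but only as an example. It does not assign groups.

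**4. Effect of placement on precision (illustration).** Assume 30/30 is reached with DT counted as dystonia, and k patients are then moved to tremor. The standard error for n patients against 30 controls, relative to 30 against 30, is sqrt(1/n + 1/30)/sqrt(2/30).

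| k (assumed) | Dystonia n | SE ratio | Tremor n | SE ratio |
|---|---|---|---|---|
| 5 | 25 | sqrt(1.100) = 1.05 | 35 | sqrt(0.929) = 0.96 |
| 10 | 20 | sqrt(1.250) = 1.12 | 40 | sqrt(0.875) = 0.94 |
| 15 | 15 | sqrt(1.500) = 1.22 | 45 | sqrt(0.833) = 0.91 |

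One contrast loses precision and the other gains it. With the standardised difference held at 0.940, ET-type power against 30 controls would be 96.1%, 97.0% or 97.6% with 35, 40 or 45 tremor patients. If patients moved the other way, it would be 92.6%, 89.1% or 82.8% with 25, 20 or 15. These figures reflect group size only. A change in mean or variance from mixing DT with ET cannot be computed from the documents.

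**The case for a change.** The strongest case for a change is that DT is foreseeable here: the background defines it and the group's prior EEG work studied it. Two analysts could place these patients differently and both claim to follow the plan. Closing the gap would take two or three sentences and one classification field per patient, and it would remove any scope for choosing the placement after seeing the data.

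Part of this stands. No sentence places these patients, the ANOVA label does not list its levels, and a line fixing both before EEG analysis would be a harmless clarification.

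The rest is weaker. Diagnosis is an entry criterion, so it is established before the EEG, and only its mapping to a group is open. That DT features in the background does not show how many such patients will enrol. The need for exclusive levels holds for a single three-level factor. If each aim were instead run as its own comparison with controls, a patient with both conditions could enter each without invalidating either model. Finally, the remedy would leave the placement to the sponsor, which concedes that none of the candidate placements is wrong.

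**Conclusion.** The observation is accurate, but it amounts to missing detail that analysts can fill sensibly. The text offers a reasonable default (DT within dystonia), the head count suggests that each patient is used once, and the three named groups resolve the loose ANOVA label. No rule or figure in the plan is shown to give a wrong result, and the stated power reproduces.

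The size is unknown because k is not given. Over an assumed k of 5 to 15, moving these patients from dystonia to tremor raises the dystonia-versus-control standard error by 5% to 22% and lowers the tremor-versus-control one by 4% to 9%. This assumes a 30/30 starting split, 30 controls, and no change in effect or variance. It is a shift of precision between two contrasts, not a bias or an error in the plan. No change is called for.
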